## 11.2 Procedures for AE Reporting

Adverse events will be assessed according to the NIH Common Terminology Criteria for Adverse Events (CTCAE) v4.0 for scale grading adverse events.

All AEs (including SAEs and UADEs) will be recorded by the investigator or designee on the appropriate electronic case report form (eCRF). Events that occur prior to the tissue harvest, including those that are considered serious, are to be recorded in the medical history. Events, including SAEs, which occur after tissue harvest procedure day, are to be recorded on the AE eCRF. The investigator will evaluate the relationship of the adverse event to both the test material and study procedure as unrelated, unlikely, possibly, probably, or definitely related and will record the findings, including all pertinent details of the event on the eCRF.

The investigator shall submit to the sponsor and to the reviewing IRB a report of any UADE occurring during an investigation as soon as possible, but in no event later than 10 working days after the investigator first learns of the effect.

In addition, the Investigator or designee will report any serious adverse events occurring during this study to the Cytori Medical Monitor as soon as possible, but no later than 24 hours after the Investigator first identifies the adverse event.

The Investigator will take appropriate measures to ensure the subject's well-being and document these measures on the appropriate eCRF.

All serious adverse events experienced will be monitored until the event has resolved, any abnormal laboratory values have returned to baseline or stabilized at a level acceptable to the Investigator and Medical Monitor, or until there is a satisfactory explanation for the changes observed.

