## 5.2 Randomization and Subject Identification

Randomization to ADRC and usual care will occur within 2 hours prior to the scheduled surgery for STSG.

Randomization will be done via an interactive web response system (IWRS). Subjects will be randomized in a 2:1 ratio to receive intravenous delivery of either Celution® System processed ADRCs with usual care or to usual care alone.

A total of up to 15 subjects will be enrolled. Each patient will contribute up to three qualified wound areas for the analysis. If more than one wound is identified, each must be noncontiguous with the other(s). Therefore, between 15 and 45 wounds will be evaluated.

The 1st 5 subjects enrolled in active treatment will be observed for adverse events over a 7 day period. If no SAEs occur during that period, for that individual subject, the next subject enrolled in active treatment may be entered with the same 7 day observation period. The safety results of the first 5 subjects will be reviewed by the DMC and their evaluation will be used in conjunction with the clinical data collected to date, and if appropriate, to potentially remove the staggering approach to the study. Enrollment after the first 5 subjects enrolled in active treatment may continue only after the DMC has completed its safety review and recommends continuation.

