## 5.3 Stopping Rules

The study will be stopped and patient enrollment will be suspended if any of the following events occur:

1. Acute cardiovascular adverse event occurring within seventy-two (72) hours of the ADRC infusion.
2. Acute allergic or anaphylactic response within seventy-two (72) hours of the ADRC infusion.
3. Acute pulmonary adverse events such as acute respiratory distress syndrome (ARDS) and renal adverse events such as acute renal failure (ARF) within seventy-two (72) hours of the ADRC infusion.

The Sponsor will notify the DMC and FDA immediately for their review and recommendation on study continuation.

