### ***8.7.1.3 Fat Harvest Stopping Rules***

The physician performing the fat harvest procedure should continuously monitor the patient for signs of significant bleeding from the puncture site(s) and overall hemodynamic stability. The tissue harvest procedure should be terminated if any of the following occur:

- Drop in systolic blood pressure < 90 mm/Hg requiring pressor support
- Profuse or uncontrollable bleeding from the puncture site(s)
- Rapid expansion of subcutaneous space at the fat cell tissue harvest site(s) related to bleeding into the subcutaneous space
- Hemoperitoneum or pneumoperitoneum
- Hemothorax or pneumothorax
- Evidence of perforation of a vascular structure that requires ligature or surgical control
- Evidence of perforation into abdominal cavity, peritoneum or gastrointestinal organ

Should any of the above occur, the fat harvest procedure should be terminated and the patient treated according to standard of care. DO NOT PROCEED WITH ADRCs ADMINISTRATION. Complete the study specific SAE form and notify the sponsor within 24 hours.

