### 13.3.4 Reporting Requirements

The following reports are required of the Investigator:

- eCRFs for each Subject entered into the study (including all screen failures)
- Reports of any SAEs or UADEs within 24 hours of becoming aware of events
- Final report at the conclusion of the study
- Progress reports to the Sponsor and IRB at regular intervals, annually at a minimum
- Report to the Sponsor, within 5 working days, of approval withdrawal by the reviewing IRB
- Report to the Sponsor and IRB of any emergency changes made to the protocol to protect the life or physical well being of a Subject no later than 5 working days after the emergency occurred

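### Section 5.3 stops the study on acute post-infusion events of any seriousness, but the 24-hour site reports and the 7-day hold are tied to serious events, so a milder stopping event can reach the sponsor late

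*Protocol*

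**What the plan says.** Section 5.3 of the protocol provides that "The study will be stopped and patient enrollment will be suspended if any of the following events occur". One event is enough. The first rule reads "Acute cardiovascular adverse event occurring within seventy-two (72) hours of the ADRC infusion" and the second "Acute allergic or anaphylactic response within seventy-two (72) hours of the ADRC infusion". The third covers acute pulmonary and renal events in the same window and names ARDS and acute renal failure only as examples. None of the three sets a condition on seriousness, CTCAE grade or relatedness. After such an event the sponsor must inform the DMC and FDA without delay. The section does not say how or when the site informs the sponsor.

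The site's reporting duties are elsewhere. Section 11.2 requires the investigator to "report any serious adverse events occurring during this study to the Cytori Medical Monitor as soon as possible, but no later than 24 hours" after identifying the event. Section 13.3.4 lists "Reports of any SAEs or UADEs within 24 hours of becoming aware of events". Section 11.1 defines a UADE by a serious effect or problem, so both duties are limited to serious events. All other adverse events go on the eCRF, with no time limit stated.

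For the first five active subjects, section 5.2 says "If no SAEs occur during that period, for that individual subject, the next subject enrolled in active treatment may be entered". The protocol summary and section 4.1 use the same condition.

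The fat-harvest stopping rules in section 8.7.1.3 end differently. For any listed event the site is told: "Complete the study specific SAE form and notify the sponsor within 24 hours".

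**The concern.** A stopping rule works only if whoever applies it learns of the trigger in time. Here the trigger is defined by type and timing of event, while the clock that brings it to the sponsor is defined by seriousness. An event can meet the first definition and not the second. Up to ten centres may take part, so another centre could infuse a subject before anyone outside the first centre knows that the trial should have stopped.

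Safety is a primary endpoint. Section 9.10 says that no other clinical trial has given ADRCs intravenously for burn wounds, and it relies on staggered entry and the DMC as safeguards.

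**Working it through.** The plan states no figure on this point, so the main check sets the passages side by side.

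**Step 1. Trigger against delivery**

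| Stopping rule | Seriousness needed to trigger? | Site-to-sponsor deadline |
|---|---|---|
| Fat harvest (8.7.1.3) | No | 24 hours for every listed event |
| Post-infusion (5.3), event is an SAE | No | 24 hours (11.2, 13.3.4) |
| Post-infusion (5.3), event is not an SAE | No | None stated |

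The third row is the gap.

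**Step 2. Can a section 5.3 event be non-serious?** ARDS, acute renal failure and anaphylaxis would normally meet the SAE definition in section 11.1. A transient arrhythmia or mild allergic reaction need not. Section 9.8 gives about 1 to 1.5 hospital days per 1% of burned TBSA. For the eligible 20% to 50% TBSA that is 20 × 1 = 20 days up to 50 × 1.5 = 75 days. A subject within 72 hours of infusion is thus typically already in hospital. A mild event then neither newly requires admission nor evidently prolongs the stay, so those criteria may not capture it.

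**Step 3. Does anything else deliver the event promptly?** Appendix A lists adverse-event assessment on Day 1 and next at the first dressing change, which has no fixed day. Routine DMC review (10.8) comes after 5, 10 and 15 subjects have at least one week of follow-up. The 7-day hold can be released when no SAE has occurred.

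**Step 4. Illustration of size.**

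- Inputs from the protocol: up to 15 subjects (4.3), 2:1 allocation (5.2), 18 months of enrolment (4.5).
- Active subjects: 15 × 2/3 = 10.
- Infusion rate: λ = 10 / (18 × 30.4375 days) = 10 / 547.9 = 0.01825 per day, a mean gap of 54.8 days across all sites.
- Chance of at least one further infusion within a lag of d days, given a qualifying event and assuming steady Poisson accrual: P = 1 − exp(−λd).

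| Assumed lag d (days) | λd | P |
|---|---|---|
| 1 | 0.018 | 1.8% |
| 7 | 0.128 | 12.0% |
| 14 | 0.256 | 22.5% |
| 30 | 0.548 | 42.2% |

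The lags are assumptions. The figures lean high during the stagger, because the next active subject then cannot enter within 7 days, and for the last active subjects, who have few or none after them.

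The chance per infused subject also needs an event rate, which the protocol does not give. At assumed rates of 5%, 10% and 20%, multiplying by P gives 0.6%, 1.2% and 2.4% for a 7-day lag, and 2.1%, 4.2% and 8.4% for a 30-day lag.

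**The case against.** The best defence is that section 5.3 binds investigators as much as section 11.2 does. Section 13.4 requires them to read and follow the whole protocol. A rule that stops the study and has the sponsor act at once presupposes that the site tells the sponsor, and section 11.2 forbids no earlier or wider report. This stands to the extent that the defect is an unstated deadline, not an instruction to withhold information.

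The SAE definition is also broad. It includes important medical events, and section 11.1 asks for judgment on whether expedited reporting is appropriate. This narrows the exposed set considerably. It does not close the gap, because the judgment is discretionary and is not linked to section 5.3.

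Other safeguards exist. The first five active subjects are spaced by 7 days, so each 72-hour window closes before the next active entry. The DMC receives all safety data, not only SAEs. Data-entry and review times may be set in the data management plan (13.3.5), which is not at hand. These points limit the size of the problem. None gives a prompt site-to-sponsor report.

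A reader might infer two stronger points that the text does not support:

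- **That sections 5.2 and 5.3 contradict each other.** They do not. Section 5.2 permits the next entry when no SAE has occurred, while section 5.3 requires suspension after a listed event. A site can obey both. The hold criterion is simply narrower than the stopping rule.
- **That the chance of at least one such event measures the harm.** At assumed rates of 5%, 10% or 20%, 1 − (1 − p)^10 gives 40%, 65% or 89% for 10 active subjects. This is the chance that an event occurs, not that someone else is infused before the sponsor hears of it, and the rates have no source in the protocol.

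**Conclusion.** The gap is real but narrow. For post-infusion events, the protocol defines its stopping trigger without regard to seriousness, yet ties both the reporting deadline and the early enrolment hold to serious events. It closes the same gap for harvest events and leaves it open for infusion events. The events at risk are mainly milder cardiovascular or allergic ones.

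Given such an event, a further infusion before the sponsor knows has a chance of about 2% at a one-day lag, rising to about 42% at 30 days. This rests on 10 active subjects, steady accrual over 18 months and lags that are assumed. Late notice is therefore possible, not certain. The mismatch in the text does not depend on these figures, and the correction is cheap enough to make before further subjects are infused.

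**What to change.** - **Reporting.** In sections 11.2 and 13.3.4, add that any event listed in section 5.3, regardless of seriousness, is reported to the Medical Monitor within the same 24 hours as an SAE. This mirrors section 8.7.1.3.
- **Hold.** Reconcile the SAE-only wording of the 7-day hold in the protocol summary and sections 4.1 and 5.2 with the stopping events in section 5.3. Which events stop the study or hold enrolment is for the sponsor to decide.
- **In the same edit.** Section 11.2 allows up to 10 working days for a UADE report, while section 13.3.4 says 24 hours. This is a separate mismatch, and the added sentence would not resolve it, so it should be settled too.

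The cost is a short protocol amendment and a few more expedited reports. No subjects, visits or procedures are added.

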## 12 EMERGENCY DEVIATION FROM THE PROTOCOL

In case of an emergency threatening the continued well being of the Subject, the Investigator may deviate from the protocol. The circumstances necessitating the deviation and the intervention(s) required will be recorded on the subject's source documentation. The Sponsor must be notified as soon as possible, but no later than 5 days after event(s) occurred. The site's Institutional Review Board (IRB) should be notified as per the IRB regulations.

## 13 REGULATORY OBLIGATIONS AND STUDY REQUIREMENTS

### 13.1 FDA and Institutional Review Board Approval

Study initiation will not take place until the following regulatory requirements are met:

- Food and Drug Administration (FDA) approval with accompanying approval letter.
- Local Institutional Review Board (IRB) full approval with accompanying approval letter.

## 13.2 Informed Consent

Written informed consent will be obtained from all subjects, or their legally authorized representative, prior to the initiation of any study specific procedures. No tests or procedures required in this protocol that are outside the standard practice for treating thermal wounds will be initiated prior to obtaining written informed consent. The original IRB approved informed consent form will be filed in the Investigator Site Files according to site procedure.

## 13.3 Monitoring Procedures and Data Management

### 13.3.1 Site Qualification

A site qualification visit will be performed to evaluate site facilities, Investigator qualifications, adequacy of staffing, and understanding of clinical and regulatory requirements.

### 13.3.2 Site Training

All Investigators and appropriate study staff will be required to participate in a site training (or initiation if appropriate) to provide orientation and training to the Celution System, the RELIEF Protocol, eCRFs and other study related documents and procedures.

### 13.3.3 Monitoring

During the course of the study, a representative of the Sponsor will make site visits to review protocol compliance, compare eCRFs and individual Subject's medical records, assess test article accountability, and ensure that the study is being conducted according to pertinent regulatory requirements. eCRF entries will be verified with source documentation. The review of medical records will be performed in a manner to ensure that Subject confidentiality is maintained.

Regulatory authorities (United States Food and Drug Administration) and/or the Sponsor's Clinical Quality Assurance Group may wish to carry out source data checks and/or on-site audit inspections. Direct access to source data will be required for these inspections and audits; they will be carried out giving due consideration to data protection and medical confidentiality.

### 13.3.4 Reporting Requirements

The following reports are required of the Investigator:

- eCRFs for each Subject entered into the study (including all screen failures)
- Reports of any SAEs or UADEs within 24 hours of becoming aware of events
- Final report at the conclusion of the study
- Progress reports to the Sponsor and IRB at regular intervals, annually at a minimum
- Report to the Sponsor, within 5 working days, of approval withdrawal by the reviewing IRB
- Report to the Sponsor and IRB of any emergency changes made to the protocol to protect the life or physical well being of a Subject no later than 5 working days after the emergency occurred

### 13.3.5 Data Management

Data management will be conducted by the Sponsor or designee, and will include a data management plan and data verification guide developed according to protocol requirements.

### **13.4 Study Center and Investigator Requirements**

To protect the rights and welfare of Subjects, the study will be conducted in conformance with the Declaration of Helsinki, the guidelines on GCPs, Code of Federal Regulations (21 CFR 11, 50, 56, 812, 814 and 820) and applicable local laws and regulations pertaining to the conduct of the study and the protection to human Subjects.

All Investigators, sub-investigators and study personnel are required to read and follow the protocol, as well as any literature that accompanies the products, prior to conducting the study procedure for the first time. In addition, all Investigators will sign and date the Investigator Statement Page of this protocol. All Investigators participating in this study will be trained in the proper use of the study procedure and in the components of the RELIEF protocol.

The Principal Investigator is ultimately responsible for the conduct of this study; however, he/she may designate a member of his/her staff to assist with the collection of data and completion of eCRFs. The designee(s) will be documented on an authorization form that is signed by the PI and kept in the Regulatory Binder, to be updated as necessary. Current copies of the authorization form will be forwarded to the Sponsor.

Obtaining informed consent in accordance with national policy is mandatory for Subject participation. All Subject data is kept confidential and procedures will be implemented to ensure that Subject confidentiality is not compromised.

If additional materials are used for screening and recruitment or provided to study Subjects (i.e. advertisements, recruitment materials) they must be approved by Cytori Therapeutics and the Institutional Review Board at the clinical site prior to use. Documentation of the approved informed consent must be provided to Cytori prior to study commencement at the clinical site.

After a Subject (or legal next of kin) has signed the Informed Consent Form, an eCRF will be initiated. After this point, the reason(s) must be documented on the report form for any Subject who has dropped, withdraws, or for any reason cannot complete this study.

#### **13.4.1 Study Center Requirements**

Due to the nature of the RELIEF Protocol, centers will be considered for participation only if they meet the following minimum facility requirements:

- Familiarity with FDA authorized IDE and/or IND Clinical Trials within the United States
- Pharmacy or laboratory (or qualified designee) capable of performing clinical trial randomization and cell dose preparation
- Ability to adhere to strict compliance with the clinical protocol for all study related procedure and observations

## 14 PUBLICATIONS

Following completion of the study, Cytori will present the study data in a clinical study report that will be delivered to the FDA according to US regulations.

When investigators external to Cytori conduct analyses of Company-sponsored study data or develop other works that use our data, we maintain the right to be informed of any plans for publication and to review any resulting works, including abstracts, presentations, or manuscripts, before they are submitted. We will return our comments to the authors in a timely manner so that they may submit the work for publication. In the event the investigator wishes to present or publish any study data (partial or complete), Cytori requests that he/she must submit the presentation / publication draft to Cytori for review prior to 30 days of the planned submission or presentation.

## 15 APPENDIX A: SCHEDULE OF PROCEDURES

	Day -2 to Day -1	Procedure Day 1	At First Dressing Change	Day 10 (±2d) 	Week 2 (±3d)	Week 3 (±3d)	Week 4 (±3d)	Week 8 (±7d)	Week 12 (±7d)	Week 26 (±14d)	Week 52 (±21d)
Informed consent	X										
Medical history (including demographics)	X										
Physical examination (including height and weight at screening)	X		X	X	X	X	X	X	X	X	X
Vital signs (BP, HR, Temp, RR)	X	X 	X	X	X	X	X	X	X	X	X
Concomitant medications	X		X	X	X	X	X	X	X	X	X
Laboratory Testing 	X	X	X								
Pregnancy test (urine)	X										
Inclusion and exclusion criteria	X										
Adverse events		X	X	X	X	X	X	X	X	X	X
Digital photography of wounds		X	X	X	X	X	X	X	X	X	X
Low Volume Lipoharvest		X									
Microbiology 		X									
ADRC dose prep and delivery		X									
% Epithelialization			X	X	X	X	X				
Biomarkers 	X		X	X	X	X	X	X	X		
% Graft Take			X	X	X	X	X				
Transepithelial water loss					X	X	X				
Wound Pain VAS			X	X	X	X	X				
Pruritis VAS						X	X	X	X	X	X
POSAS questionnaires						X	X	X	X	X	X
Vancouver Scar Scale									X	X	X
Skin elasticity measurement									X	X	X

	Day -2 to Day -1	Procedure Day 1	At First Dressing Change	Day 10 (±2d)	Week 2 (±3d)	Week 3 (±3d)	Week 4 (±3d)	Week 8 (±7d)	Week 12 (±7d)	Week 26 (±14d)	Week 52 (±21d)
Skin pigmentation									X	X	X
Skin hardness									X	X	X
Complete Wound Closure					X	X	X	X	X		
Randomization		X									

Day 10 assessments performed only if wound dressing is being changed between days 8 and 12. Vital signs will be monitored according to institutional procedures. Microbiological testing of dose samples (ADRCs) at baseline (prior to ADRCs administration). Biomarkers will be measured in serum from 4 to 5 ml of whole blood that is collected, centrifuged, separated into 500-µL aliquots, and stored at -80°C will be collected at baseline (prior to ADRC administration), days 5 and 10 and weeks 2, 3, 4, 8 and 12 post ADRC administration.  Laboratory testing will include CBC with Platelets, INR, PTT, Electrolytes, alkaline phosphatase, AST, ALT, bilirubin, total protein, albumin, BUN and creatinine and, for patients with diabetes only, evaluation of HbA1c levels (see Exclusion Criterion 10).

